4. Application of univariable and multivariable logistic regression that uses sputum eosinophils, blood eosinophils, FENO and serum periostin, as well as bronchodilator reversibility, measures of atopy, and other phenotypic characteristics from both eosinophilic and non-eosinophilic participants to construct ROC curves and c (concordance) statistics to identify “cutpoints” for each biomarker (which also can be compared with previously suggested cutpoints) to examine the value of these biomarkers as predictors of response to treatments.

All of the analyses described above will follow the intention-to-treat paradigm whereby all available data from randomized participants are included in the analyses regardless of information about deviations from study protocol.

D. Statistical Analysis Plan for Additional Secondary Outcomes

We will analyze separately each of three components of the composite outcome as secondary outcomes. We will apply a proportional hazards regression analysis for the time to treatment failure, with a random effect term (frailty) for the SIENA participant to account for the correlations within the SIENA participant ²⁷. The proportional hazards regression model will include fixed terms for treatment regimen, sequence, period, and season of enrollment and an additional random effect term for clinical site. We will apply a linear mixed-effects model for longitudinal data on ACDs and FEV₁. The statistical model will include

(1) fixed effects for treatment regimen, sequence, period, and season of enrollment (spring, summer, fall, winter) nested within each of the eosinophilic and non-eosinophilic phenotypes. (2) a random effect for clinical site within each of the eosinophilic and non-eosinophilic phenotypes, and (3) a 7×7 unstructured variance-covariance matrix for the seven measurements per participant (baseline and two timepoints within each of the three periods). We will apply a similar statistical approach for the other secondary outcomes that are measured on a continuum, such as diary peak flow values and logarithmic-transformed methacholine challenge PC_{20} . We will analyze time to asthma exacerbation in a manner similar to that for time to treatment failure.

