The AsthmaNet Steering Committee will monitor SIENA recruitment and continually reevaluate the likelihood of completing recruitment by May 2016. Depending on the results of this evaluation, the Steering Committee may recommend to the DSMB that a switch to MDI should be made. If a switch is made, all participants will complete the study using whichever formulation they receive at randomization. No participants will switch from DPI to MDI during the course of the study. The randomization plan and the statistical analysis plan will be modified accordingly. In particular, we will insert an additional level of stratification for randomization according to DPI/MDI assignment. The current statistical plan is to include the stratifying variables as blocking factors, so DPI/MDI assignment will be included as a blocking factor in the statistical

analysis.

Update November 2015: Due to lagging recruitment and mometasone DPI expiration issues, a switch to mometasone MDI is necessary. *Merck* has provided mometasone and mometasone placebo in the form of Asmanex® HFA, 200 mcg/puff. Participants will take 1 puff twice daily (total dose active drug = 400 mcg). *Merck* will coordinate the blinding of drug with information provided by the DCC. A third-party packager will label with additional regulatory information.

Contingent Statistical Analysis

Because SIENA invokes a three-way crossover design, a stratified randomization based on prognostic factors is not critical. Instead, we only will invoke clinical site within phenotype (eosinophilic, non-eosinophilic) as a stratifying variable with permuted blocks of size six (one complete cycle of the six). As indicated above, if a DPI/MDI switch occurs, then we will include this as another stratification variable. In particular, the stratification will be according to DPI/MDI status nested within clinical center, which is nested within phenotype.

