The statistical analysis plan for the primary and secondary outcomes is described in Section VIII.C. With respect to the primary outcome variable, we will apply a linear mixed-effect model that includes (1) fixed effects for treatment regimen, sequence, period, and season of enrollment (spring, summer, fall, winter) nested within each of the eosinophilic and non-eosinophilic phenotypes, (2) random effects for clinical site within each of the eosinophilic and non-eosinophilic phenotypes, and (3) a 7×7 unstructured variance-covariance matrix for the seven measurements per participant within each of the eosinophilic and non-eosinophilic phenotypes. We will account for the additional stratifying variable of DPI/MDI status by including it as another fixed-effect variable in linear mixed-effects model.

Obviously, completion of the entire study with the same manufacturer's lot of active drug and placebo is ideal. However, if *Merck* is not able to provide us with sufficient placebo DPI, we do not believe that the switch from active DPI to active MDI will negatively impact the scientific validity of the study.

The goal of the study is to examine whether subjects with *mild-to-moderate asthma* who are persistently non-eosinophilic require a different treatment strategy than those with sputum eosinophilia. Preliminary data suggest that subjects without sputum eosinophilia (presumed "TH2-low" asthma) do not respond to inhaled corticosteroids or to prednisone. In SIENA we will enroll subjects with persistent asthma who meet the EPR-3 criteria for *Mild-to-Moderate Asthma* and for whom *Step 2 Treatment* (Preferred = Low-dose ICS) is recommended. However, because we believe that ~50% of these subjects will not respond to ICS, we will provide *Step 3 Treatment* (Medium-dose ICS), to ensure that the issue is not too little ICS. In the case of Mometasone, EPR-3

defines "low-dose" as 200 mcg/day and "medium dose" as 400 mcg/day. Because Merck will be fulfilling FDA criteria for equivalence, we anticipate that the doses delivered will be comparable, but even if there is a small difference in dose delivered between the DPI and MDI preparations, that dose should be sufficiently high on the flat portion of the dose-response curve that it will not impact the outcome.

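### Section VIII.D, as written, gives the continuous secondary outcomes one covariance matrix for both phenotypes, while Appendix D writes the same model terms with a matrix per phenotype; eosinophilic standard errors are wrong if the covariances differ

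*Combined protocol and SAP*

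**What the plan says.** Section VIII.D (additional secondary outcomes) sets out a three-part model: "We will apply a linear mixed-effects model for longitudinal data on ACDs" and FEV1, with a similar approach for the other continuous secondary outcomes.

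- Part (1): fixed effects for treatment, sequence, period and season, "nested within each of the eosinophilic and non-eosinophilic phenotypes".
- Part (2): "a random effect for clinical site within each of the eosinophilic and non-eosinophilic phenotypes".
- Part (3): a 7×7 "unstructured variance-covariance matrix for the seven measurements per participant (baseline and two timepoints within each of the three periods"), with no mention of phenotype.

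Appendix D, under Contingent Statistical Analysis, lists the same three parts, but its third is a 7×7 "unstructured variance-covariance matrix for the seven measurements per participant within each of the eosinophilic and non-eosinophilic phenotypes". It handles the dry-powder/metered-dose (DPI/MDI) stratum by "including it as another fixed-effect variable in linear mixed-effects model". It introduces the model with these words: "With respect to the primary outcome variable, we will apply a linear mixed-effect model that includes". The contingency was triggered in November 2015: "Due to lagging recruitment and mometasone DPI expiration issues, a switch to mometasone MDI is necessary".

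Section VIII.C analyses the primary outcome differently. It is a pairwise preference between two treatments, tested within phenotype by exact binomial tests and between phenotypes by Fisher exact tests.

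**The concern.** Two of the three parts of the VIII.D list carry the phenotype qualifier and the third does not, so the natural reading is one covariance matrix shared by both phenotypes. Appendix D says otherwise for the same terms, and nothing states which version governs control days and FEV1.

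The choice matters because the groups are unequal. A shared matrix is close to a size-weighted average, so the larger non-eosinophilic (EOS-) group dominates it. If eosinophilic (EOS+) participants vary more, the model reports EOS+ standard errors that are too small. If they vary less, it reports them too large and power is lost.

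The documents do not support equal covariances, and they give some reason for doubt. The EOS+ stratum combines persistent and intermittent eosinophilia. The background section reports different mean FEV1 changes after intensive treatment: 8.6% in the persistent, 4.7% in the intermittent and -0.2% in the non-eosinophilic subgroup. Mixing different responses can widen the variance of a treatment contrast. It does not fix the size or the direction of the net difference.

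**Working it through.** **The plan's own figures.** VIII.G gives 74 + 262 = 336 participants. Its co-primary power of 0.90 reproduces: 262 × 0.85 (drop-out) × 0.70 (non-ties) = 156 informative participants, p = 0.45/0.70 = 0.643, and a two-sided exact binomial test at 0.025 has power 0.9025. That test uses no covariance matrix. The documents give no standard deviation, covariance, power or precision for the mixed model, so there is no figure to reproduce there.

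**Weights in a pooled matrix.** EOS- 262/336 = 78.0%; EOS+ 74/336 = 22.0%. Equal 15% drop-out in both groups leaves these unchanged.

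**Effect on standard errors.** Let r be the EOS+ variance of a treatment contrast divided by the EOS- variance. This is an assumption, shown as a range. With proportional covariances and complete data, in units of the EOS- variance:

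- pooled variance = (262 + 74r)/336
- EOS+ contrast: model SE / true SE = √(pooled/r)
- EOS- contrast: √pooled
- phenotype difference: √[pooled × (1/262 + 1/74) / (1/262 + r/74)]
- actual error of a nominal two-sided 5% test = 2 × [1 − Φ(1.96 × ratio)]

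Example, r = 1.5: pooled = (262 + 111)/336 = 1.110. The EOS+ ratio is √(1.110/1.5) = 0.860, and the error is 2 × [1 − Φ(1.686)] = 9.2%.

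| r | EOS+ SE ratio | EOS+ error | EOS- error | Difference error |
|---|---|---|---|---|
| 0.5 | 1.33 | 0.9% | 6.5% | 1.8% |
| 0.67 | 1.18 | 2.1% | 5.9% | 2.9% |
| 1 | 1.00 | 5.0% | 5.0% | 5.0% |
| 1.25 | 0.92 | 7.2% | 4.4% | 6.6% |
| 1.5 | 0.86 | 9.2% | 3.9% | 8.0% |
| 2 | 0.78 | 12.6% | 3.0% | 10.5% |

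**Simulation check.** The three-period, seven-measurement design was simulated with 63 EOS+ and 223 EOS- completers (74 × 0.85 and 262 × 0.85), an assumed within-person correlation of 0.8, critical value 1.98 and 2,000 runs per ratio.

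- Pooled matrix: EOS+ error 0.6%, 5.4%, 9.3% and 13.0% at r = 0.5, 1, 1.5 and 2, in line with the formula.
- Separate matrices without a small-sample correction: EOS+ error between 6.4% and 8.3% over the same ratios.

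**Parameters.** One unstructured 7×7 matrix has 7 × 8/2 = 28 parameters; two have 56.

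**The case against.** The strongest reply has four parts.

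- **The harm is hypothetical.** No variances are given, and at a ratio of 1 nothing changes. The trial's premise is that mean response differs by phenotype, and VIII.D already separates the means. This stands: neither the size nor the direction of any error can be established from the documents.
- **The reach is narrow.** The secondary research question concerns preference and is tested by exact methods. VIII.D names no test of phenotype difference for control days or FEV1. This stands too, so the difference column applies only if such a contrast is drawn from the model. The phenotype-nested treatment effects do yield EOS+ contrasts directly.
- **Appendix D names the primary outcome, so it may be a different analysis.** This does not stand. A preference between two treatments has no seven repeated measurements, so the Appendix D model can sensibly apply only to the VIII.D outcomes. The label is itself an error to reconcile.
- **Separate matrices cost stability.** They double the parameters with about 63 EOS+ completers. Without a correction, their simulated EOS+ error (6.4% to 8.3%) is worse than pooling when variances are equal, and no clear gain over the pooled 7.2% at a ratio of 1.25. This stands, and it is why the fix needs a small-sample method.

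The device term is largely settled already. Appendix D commits to it, and VIII.C includes it in the logistic sensitivity analysis. No participant changes device, so little effect on within-person contrasts is expected. Its absence from VIII.D is a matter of consistency.

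**Conclusion.** The point holds as a cheap improvement. VIII.D item (3), as written, specifies a single matrix while Appendix D makes it phenotype-specific for the same terms. EOS- participants supply 78% of a pooled matrix, so EOS+ contrasts on the continuous secondary outcomes are mis-calibrated whenever the phenotype covariances differ. Over assumed variance ratios of 0.67 to 2, a nominal 5% EOS+ test runs at about 2.1% to 12.6%. These figures assume proportional covariances and complete data.

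A reader might infer three stronger things that the documents do not support:

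- That the secondary intervals are wrong whatever the truth. They are correct if the covariances are equal, and VIII.D omits the qualifier rather than asserting equality.
- That the EOS- group fixes the EOS+ error bars. It dominates the matrix, but EOS+ contributes 22% and each group's own size still enters its standard error.
- That the trial's main phenotype conclusions are at risk. The co-primary binomial tests and the phenotype Fisher tests do not use this matrix.

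**What to change.** 1. In VIII.D item (3), adopt Appendix D's wording: a 7×7 "unstructured variance-covariance matrix for the seven measurements per participant within each of the eosinophilic and non-eosinophilic phenotypes".
2. Specify a small-sample method for standard errors and degrees of freedom, such as Kenward-Roger.
3. State in advance that if the EOS+ matrix does not converge, a simpler structure will be used that is still phenotype-specific.
4. Carry the DPI/MDI fixed effect into VIII.D for consistency with Appendix D.
5. Correct the Appendix D label so that the linear mixed model is attached to the VIII.D continuous outcomes and not to the primary outcome.

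The cost is wording only. The downside is 28 more covariance parameters and a slightly less stable EOS+ fit, with a small loss if the covariances are in fact equal.

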An important exploratory question is whether other biomarkers such as blood periostin, blood eosinophils or eNO can be used instead of sputum eosinophils to identify patients with differential treatment preferences to ICS and LMA. Although recent data suggest that airway eosinophilia, elevated FeNO, and serum periostin may all be markers of TH₂ inflammation, we have chosen to stratify our populations based on sputum eosinophilia, a robust biomarker that has been well-characterized. Periostin, a 90 kD protein produced by airway epithelium in response to IL-13, is an alternate candidate biomarker, but more information is needed about how blood periostin levels relate to airway eosinophil levels, and about the threshold value for defining abnormal periostin levels. FeNO is another candidate biomarker of airway eosinophilia and ICS responsiveness but two recent reports have questioned its utility as a biomarker of airway eosinophilia ^{1, 19}. In this prospective study we propose to collect serum for periostin and measure eNO and blood eosinophils so that we can evaluate the relative utility of these three simpler tests as biomarkers of airway eosinophilia and ICS treatment response in mild moderate asthma. We also propose to assess the bronchodilator response (BR) to both beta agonist and

[figure not shown]
anticholinergic agents to determine whether the eosinophil-negative group has different bronchodilator responses to albuterol vs. ipratropium (Atrovent® HFA). We will include adolescents 12-18 years old in this study because asthma guidelines combine this group with adults, but the study will not be powered for the comparison between adults and adolescents. This important exploratory analysis will provide clues as to the prevalence of eosinophil negative asthma in adolescents, the utility of and appropriate cut point for periostin, and the similarity or difference in the treatment response between adolescents and adults.

Additional exploratory outcomes include a number of tools and endpoints to characterize the time course of asthma exacerbations. The Protocol Review Committee previously suggested that AsthmaNet trials be used to gather preliminary information on exacerbations, as was also suggested in a recent NIH Outcomes Workshop ²⁰. These assessments will be incorporated within the main SIENA protocol and visit structure, to minimize both participant and site burden, and to enhance safety follow-up.

IV. PROTOCOL OVERVIEW

A. Protocol Design

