The co-primary research hypotheses are that within the non-eosinophilic phenotype, ICS is superior to placebo and LMA is superior to placebo. In statistical terms, the null hypotheses are

- (1) $H_0: p_{Eos-, ICS > Placebo} = p_{Eos-, Placebo > ICS}$
- (2) $H_0: p_{Eos-, LMA > Placebo} = p_{Eos-, Placebo > LMA}$

Since $p_{Eos-,ICS \approx Placebo}$, $p_{Eos-,LMA \approx Placebo}$, $p_{Eos+,ICS \approx Placebo}$, and, $p_{Eos+,LMA \approx Placebo}$ do not factor into the null hypotheses, participants who do not have a differential response (i.e., treatment was equivalent to placebo) will not be included in the analyses. We will apply two-sided, exact binomial tests at the 0.025 significance level (Bonferroni correction) for each of these null hypotheses. To assess potential period and seasonal effects, a sensitivity analysis will be performed by applying logistic regression models to those who had a differential response (i.e., the treatments were not equivalent), with covariates to adjust for period differences, season of enrollment, and ICS delivery (DPI/MDI).

Secondary analyses with the primary outcome include the following:

1. Comparisons within the eosinophilic phenotype in terms of the null hypotheses $H_0: p_{Eos+,ICS > Placebo} = p_{Eos+,Placebo > ICS}$ and $H_0: p_{Eos+,LMA > Placebo} = p_{Eos+,Placebo > LMA}$, which we will test via two-sided, exact binomial tests at the 0.025 significance level (Bonferroni correction) for each of these null hypotheses.
2. Comparisons between the non-eosinophilic and eosinophilic phenotypes in terms of the null hypotheses $H_0: p_{Eos-,ICS > Placebo} = p_{Eos+,ICS > Placebo}$ and $H_0: p_{Eos-,LMA > Placebo} = p_{Eos+,LMA > Placebo}$, which we will test via two-sided, 0.025 significance level Fisher exact tests (Bonferroni correction).
3. Comparison of the ICS and LMA treatments in the manner described above for the primary and secondary analyses (within the non-eosinophilic

phenotype, within the eosinophilic phenotype, and between the eosinophilic and non-eosinophilic phenotypes, respectively).

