We will pursue additional secondary analyses to investigate whether baseline measurements of the biomarkers (blood eosinophils, periostin, and exhaled nitric oxide) significantly predict any of these secondary outcomes. We will achieve this by including the biomarkers in the statistical models described in the previous paragraph.

Finally, we will perform exploratory subgroup analyses of the primary and secondary outcomes within levels of gender, minority status, age group, baseline BMI, and baseline FEV_1 .

E. Missing Data

Because of the possibility of drop-outs and other missed visits, there will be some missing data. The statistical models and analyses that are planned for the

primary and secondary outcomes assume that the data are missing-at-random (MAR). Because we are applying likelihood-based methods for the data adjustment with primary outcome and for all of the secondary outcomes, MAR data still yield valid estimates. Although not expected, if it appears that the MAR assumption is not reasonable, then we will invoke shared parameter models to simultaneously model the time to drop-out and the individual secondary outcome²⁸.

F. Interim Analyses

There will be no formal interim analysis of efficacy in this trial. Nevertheless, interim statistical analyses to evaluate the safety of the three treatment regimens will be presented to the AsthmaNet Data and Safety Monitoring Board (DSMB) semi-annually for review. Based on the results of these interim analyses, the DSMB will recommend to the NHLBI the continuation or discontinuation of the trial. In addition, the DSMB will be monitoring all of the safety data throughout the course of the trial and will be notified within 72 hours of any serious adverse event (SAE) that is deemed both unexpected and related to the study. All SAEs will be reviewed at each 6-month review.

G. Power Calculations

The target sample for the SIENA trial is 336 randomized participants, 74 in the eosinophilic phenotype and 262 in the non-eosinophilic phenotype, because we anticipate a 1-to-3.5 ratio, or smaller, of the eosinophilic phenotype to the non-eosinophilic phenotype.

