For the co-primary comparisons within the non-eosinophilic phenotype, the sample size of 262 yields statistical power of 0.9 with two-sided, 0.025 significance level tests (Bonferroni correction), while allowing for a 15% drop-out rate, to detect $p_{Eos-,ICS>Placebo} - p_{Eos-,Placebo>ICS} = 0.20$ (and to detect $p_{Eos-,LMA>Placebo} - p_{Eos-,Placebo>LMA} = 0.20$). We assume that 30% of the participants will not display a preference for ICS versus placebo and therefore not included in the primary analysis (and that 30% of the participants will not display a preference for LMA versus placebo). The following table illustrates the level of statistical power for selected sample sizes.

N	$p_{Eos-,ICS \approx Placebo}$ or $p_{Eos-,LMA \approx Placebo}$	$p_{Eos-,ICS>Placebo} - p_{Eos-,LMA>Placebo}$ or $p_{Eos-,Placebo>ICS} - p_{Eos-,Placebo>LMA}$	Statistical Power
	0.30	0.20	
202	0.30	0.20	80%
228	0.30	0.20	85%
262	0.30	0.20	90%

With respect to the secondary analysis of the primary outcome, the following table illustrates the statistical power for detecting $p_{Eos+,ICS>Placebo} = 0.71$ and $p_{Eos-,ICS>Placebo} = 0.45$, yielding a difference of 0.26 between the two phenotypes (and for detecting $p_{Eos+,LMA>Placebo} = 0.71$ and $p_{Eos-,LMA>Placebo} = 0.45$, yielding a difference of 0.26 between the two phenotypes).

EOS-Negatives		EOS-Positives			Statistical Power
N	$p_{Eos-,ICS>Placebo}$ or $p_{Eos-,LMA>Placebo}$	N	$p_{Eos+,ICS>Placebo}$ or $p_{Eos+,LMA>Placebo}$		
202	0.45	58	0.71		80%
228	0.45	66	0.71		85%
262	0.45	74	0.71		90%

For the secondary analysis of comparing the ICS and LMA treatments within the non-eosinophilic phenotype, there is 90% statistical power with a sample size of 262 to detect a difference of 0.185 ($= p_{Eos-,LMA>ICS} - p_{Eos-,ICS>LMA}$) with a two-sided, 0.05 significance level test.

H. Anticipated Results

Our primary hypothesis is that the response to ICS and LMA will be different in participants with and without airway eosinophilia. We anticipate that ICS will be more effective in asthmatics with airway eosinophilia and that LMA will be more effective in asthmatics who are persistently non-eosinophilic.

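### The exploratory subgroup analyses are planned only inside each level, with no comparison between levels, although the age analysis is meant to compare adolescents with adults

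*Combined protocol and SAP*

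**What the plan says.** The last paragraph of section VIII.D announces "exploratory subgroup analyses of the primary and secondary outcomes within levels of gender, minority status, age group, baseline BMI" and baseline FEV1. It names no test, significance level, interaction term or comparison between levels. The proportional hazards and mixed models described earlier in VIII.D contain no regimen-by-subgroup term.

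Section III.J gives the purpose of the age analysis. "We will include adolescents 12-18 years old in this study", it says, and the analysis should offer clues to, among other things, "the similarity or difference in the treatment response between adolescents and adults". It also warns that "the study will not be powered for the comparison between adults and adolescents".

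For eosinophil phenotype the plan is fuller. Section VIII.C lists exact binomial tests inside each phenotype and, as a separate item, Fisher exact tests between the two phenotypes. Item 4 of the same list plans logistic regression of treatment response on biomarkers, reversibility, atopy and other, unnamed phenotypic characteristics. It does not name age, gender, minority status or BMI.

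**The concern.** Whether adolescents and adults respond alike is a question about the difference between two treatment effects. An analysis confined to each level estimates the two effects but not their difference. The plan recognises this for eosinophil phenotype, where it adds the between-group step, but the subgroup sentence stops after the first step.

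Without a stated between-level comparison, the natural shortcut is to see which level reaches significance. When one level is small, it will often miss significance even though its effect equals that of the larger level. An active drug could then appear to work in adults and not in adolescents because of subgroup size alone. The same applies to the other four factors.

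**Working it through.** **Inputs from the documents**
- "336 randomized participants, 74 in the eosinophilic phenotype and 262 in the non-eosinophilic phenotype" (VIII.G).
- "the sample size of 262 yields statistical power of 0.9", "while allowing for a 15% drop-out rate" (VIII.G).
- Two-sided level 0.025 for each co-primary test: "We will apply two-sided, exact binomial tests at the 0.025 significance level (Bonferroni correction) for each of these null hypotheses" (VIII.C).
- Difference in preference probabilities 0.20, and 30% with no preference (VIII.G).

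**Assumptions**
- Adolescent share: not in the documents; 10%, 20% and 30% are used, with 50% as the even-split case.
- Level for subgroup tests: not in the documents; 0.05 and 0.025 are both shown.
- Test inside each level: the primary exact binomial test, for illustration.

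**Step 1: reproduce the plan's power.** With 30% ties, the two preference probabilities sum to 0.70 and differ by 0.20, so they are 0.45 and 0.25. Among those with a preference, p = 0.45/0.70 = 0.643. The number analysed is 262 × 0.85 × 0.70 = 155.9, about 156. The exact two-sided binomial test against 0.5 at 0.025 has power 0.903, against 0.90 stated. Averaged over a random number of ties, N = 228 gives 0.853 and N = 202 gives 0.801, against 85% and 80% stated. The inputs are therefore read as the plan intends.

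**Step 2: the same effect in both levels.** Split the 156 into adolescents and adults, both with p = 0.643. The levels contain different people, so the tests are independent. With power a in adolescents and b in adults,

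P(one significant, the other not) = a(1 − b) + b(1 − a).

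For a 20% share at 0.05: 0.282 × 0.101 + 0.899 × 0.718 = 0.028 + 0.645 = 0.67.

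| Share | Adolescents / adults | a, b at 0.05 | Disagree, 0.05 | a, b at 0.025 | Disagree, 0.025 |
|---|---|---|---|---|---|
| 10% | 16 / 140 | 0.12, 0.91 | 81% | 0.12, 0.87 | 78% |
| 20% | 31 / 125 | 0.28, 0.90 | 67% | 0.17, 0.82 | 71% |
| 30% | 47 / 109 | 0.47, 0.82 | 52% | 0.35, 0.76 | 58% |
| 50% | 78 / 78 | 0.65, 0.65 | 45% | 0.57, 0.57 | 49% |

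The exact test moves in steps. A 10% share is 15.6 people, and rounding down to 15 / 141 gives 79% at 0.05 and 82% at 0.025. At 0.05, the specific pattern of adults significant and adolescents not has probability 80% at a 10% share (16 / 140) and 65% at 20%.

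**Step 3: dependence on the common effect** (20% share):

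| Common effect | 0 | 0.10 | 0.15 | 0.20 | 0.30 |
|---|---|---|---|---|---|
| Disagree, 0.05 | 8% | 38% | 62% | 67% | 39% |
| Disagree, 0.025 | 3% | 25% | 53% | 71% | 55% |

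Disagreement is rare when neither level has an effect. It peaks near the design effect and falls again once the small level also has good power.

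**Step 4: a direct comparison.** A Fisher test of the preference proportion, adolescents against adults, at nominal 0.05 and with identical effects, declares a difference in 3.7%, 3.7% and 4.2% of trials (15, 31 and 47 adolescents). If adolescents truly had no effect (p = 0.50) while adults had p = 0.643, its power would be about 16% at a 10% share and 28% at 20%. It holds its error rate but has low power.

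**The case against.** A reader might infer that the plan repeats the primary test in each level and contrasts the verdicts, so that the trial will report benefit in adults and none in adolescents. The text does not support this. VIII.D names no test and no rule for comparing levels, and level-specific estimates with intervals would also fit its wording. The defect is an omitted comparison. The misleading contrast is something a later reader might make.

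A reader might also infer that the levels will usually look different whatever the effect. That does not hold either. It needs a common effect near the design value and a minority adolescent group, and the documents give no adolescent share. Sections V.A and IX.B even state a belief that non-eosinophilic participants will not respond to ICS, although hypothesis III.E.1 says otherwise. With no effect, the ICS verdicts would rarely disagree.

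Three further points stand in the plan's favour. The analyses are labelled exploratory, the lack of power is disclosed, and the effect modifier central to the trial has its own between-group test. The figures above also cover only the composite outcome in non-eosinophilic participants, whereas VIII.D does not restrict the subgroups that way.

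Two replies remain. Disclosing low power does not supply a method that answers III.J's question, and low power in the small level is what creates the misleading pattern. The regression in VIII.C item 4 could serve, because the response is a within-person preference, but only if the subgroup factors were named in it.

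**Conclusion.** The point holds as a minor one. The stated analysis estimates effects inside each level, while III.J asks about the difference between levels, and no between-level comparison is specified for any of the five factors. This does not depend on the simulated sizes.

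The size of the possible misreading is conditional. It is 52% to 81% disagreement at 0.05 and 58% to 78% at 0.025, given an identical effect of 0.20, about 156 non-eosinophilic participants with a preference, an assumed adolescent share of 10% to 30%, and a reader who compares significance across levels. For an even split it is 45% and 49%. At zero effect it is about 3% to 8%.

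No primary or secondary conclusion, sample size or safety matter is affected. Analysing BMI and FEV1 by level rather than continuously is a modelling choice, and the documents show no error in it.

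**What to change.** Amend the subgroup sentence in VIII.D as follows.

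- **Composite outcome.** For each factor, add it as a covariate in the preference logistic regression already described in VIII.C. Because the response is which regimen the participant did better on, that coefficient is the treatment-by-subgroup interaction. A Fisher comparison of preference between levels, as already planned for phenotype, is an acceptable alternative.
- **Component and other secondary outcomes.** Add a regimen-by-subgroup term to the mixed and hazard models.
- **Reporting.** Give level-specific estimates and the interaction estimate, all with confidence intervals. Base any statement of difference on the interaction alone. Do not read a non-significant interaction as evidence of similarity.
- **Labels.** Keep the exploratory label and the statement about power. Define the age groups, because III.J counts adolescents as 12 to 18 while the smoking criterion in V.C divides at 18.

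Continuous modelling of BMI and FEV1 is optional.

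The cost is a few sentences of SAP text and one extra term per factor and model. The interaction intervals will be wide: as Step 4 shows, the comparison will seldom settle the question, and the intervals will make that visible.
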